13.2 Sample size determination

No formal hypothesis tests are required. However, in order to inform a future trial, the recruitment rate, that is, the proportion of patients who are randomised relative to those who are eligible and approached, will be calculated. One hundred recruited patients will allow us to estimate a recruitment rate of 50%, with a 95% CI of 43% to 57%, a standard error of 3.5%.

13.3 Clinical Study Report

At appropriate intervals, interim data listings will be prepared to give the Investigators the possibility to review the data and check the completeness of information collected. All clinical data will be presented at the end of the trial on final data listings. The Sponsor will prepare a Clinical Study Report (CSR) based on the final data listings. The report will be submitted to the Investigator(s) for review and confirmation it accurately represents the data collected during the course of the trial. Summary results of the trial will be provided by the Sponsor to the Regulatory Authority (MHRA) and to the Research Ethics Committee.

14 DATA MANAGEMENT

The plan for the data management of the trial are outlined below. Further details of the data management aspects of the study will be fully documented in a comprehensive Data Management Plan (DMP) authored by the trial Clinical Data Manager (CDM).

14.1 Source data

Source documents are where data are first recorded, and from which patients' eCRF data are obtained. These include but are not limited to: primary or secondary care records (from which medical history and previous and concurrent medication may be summarised into the CRF), clinical and office charts, laboratory and pharmacy records, diaries, microfiches, radiographs, and correspondence. For some data, the data will be recorded directly into the eCRF and therefore acts as both source and CRF. All documents will be stored safely in confidential conditions. On all trial-specific documents, other than the signed consent, the patient will be referred to by the trial patient number/code, initials, not by name.

Patients will be given the option of using the Medidata patient app in addition to a paper diary card, to record their vital signs and responses to the questionnaire. Separate consent, covering data protection, will be collected for all patients who choose to use the app. Data entered in the app will be considered source and uploaded directly into the database.

The DMP will clearly state which data is entered directly into the eCRF and which data is derived from other source documents for entering.

14.2 Access to data

Direct access will be granted to authorised representatives from the Sponsor, host institutions and the regulatory authorities to permit trial-related monitoring, audits and inspections.

14.3 Data recording and record keeping

The eCRF for this trial will be a RAVE clinical database. As per Section 14.1, source data may be separate documentation/diaries/records, however the eCRF itself may also act as a source for certain data items. As per the DMP, source documents will be clearly stated and the Sponsor may ask that certified copies are scanned/posted as appropriate for source data verification in a timely fashion, as it is anticipated that on-site monitoring visits may not be possible due to restrictions at sites.

The Investigator and/or Sponsor must retain copies of the essential documents for a minimum of 25 years following the end of the trial.

During the clinical trial and after trial closure the Investigator must maintain adequate and accurate records to enable both the conduct of a clinical trial and the quality of the data produced to be evaluated and verified. These essential documents (as detailed in Chapter V of Volume 10 (Clinical Trials) of The Rules Governing Medicinal Products in the European Union based upon Section 8 of the ICH GCP Guidelines), including source documents such as worksheets, scans, hospital records, diary cards, trial related documents and copies of the e/CRFs, associated audit trail and serious adverse event (SAE) report forms, shall show whether the Investigator has complied with the principles and guidelines of Good Clinical Practice (GCP).

All essential documents required to be held by the Investigator must be stored in such a way that ensures that they are readily available, upon request, to the Regulatory Agency or Sponsor, for the minimum period required by national legislation or for longer if needed by Sponsor. Records must not be destroyed without prior written approval from Sponsor.

The medical files of trial subjects shall be retained in accordance with national legislation and in accordance with the maximum period of time permitted by the hospital, institution or private practice.

14.3.1 Recording of daily calls

During the trial, patients will be asked for permission and consent to record their daily video (phone) calls with the clinical trial team. Patients will be asked to consent during main trial consent and to also confirm consent verbally before each video/phone call begins. After each call is completed, the recording will immediately be emailed to a secure NHS email for storage on a secure NHS server. The recording will be deleted thereafter from the original recording device. Each NHS Trust/Board will be responsible for the security and confidentiality of these recordings. These recordings will not be shared with the Sponsor to protect the patient's confidentiality. The NHS Trust/Board will be solely responsible for the recording, transfer, storage and deletion of the recording. All recordings will be deleted from the NHS secure server at the end of the trial.

This is not a requirement of trial participation but a proposed way of supporting the patient's participation on the trial.

15 QUALITY CONTROL AND QUALITY ASSURANCE PROCEDURES

15.1 Risk assessment

A risk assessment and monitoring guidelines will be prepared before the trial opens and will be reviewed periodically throughout the trial to reflect significant changes to the protocol or monitoring activities.

15.2 Monitoring

In order to ensure that quality data is collected and that sites are adhering to the protocol, ICH GCP and other guidelines and local regulations, data will be monitored at regular intervals by the Sponsor.

The level of monitoring will be informed by the trial specific risk assessment and captured in the trial monitoring plan.

The Investigator and clinical trial teams will be responsible for entering trial data into the eCRF and providing certified copies of source data where applicable to facilitate source data verification. It is the Investigator's responsibility to ensure the accuracy of the data entered into any source document provided to the Sponsor, and to ensure that any patient data provided to the Sponsor is suitably anonymised.

Once source documents have been completed by site staff they will be scanned and emailed to the Sponsor. Any missing data or any data that requires querying with the site staff will be raised by the Sponsor.

Movement of people may be restricted, therefore, monitoring of patient medical records will be completed remotely where possible in accordance with the trial-specific monitoring plan.

Monitoring of the data will occur as the data is being entered into the database.

In order to verify that the trial is conducted in accordance with ICH GCP, regulatory requirements, and the trial protocol, and that the data is authentic, accurate and complete, source data will be verified.

Upon trial completion, a Closedown Visit will be conducted.

15.3 Quality assurance

The Sponsor will assess each trial site to verify the qualifications of each Investigator and the site staff and to ensure that the site has all of the required equipment. A Study Initiation meeting will occur where among other things the Investigator will be informed of their responsibilities and procedures for ensuring adequate and correct trial documentation. During this meeting, training will be provided to the investigator and the local study team, in accordance with the study-specific monitoring plan.

The Investigator is required to prepare and maintain adequate and accurate case histories designed to record all observations and other data pertinent to the trial for each patient. Trial data for each enrolled patient will be entered into the Source Worksheets by study site personnel.

15.4 Protocol deviations and amendments

The protocol should be adhered to throughout the conduct of the trial, if a situation arises where the conduct of the trial may not be in line with the protocol, then site should contact the Sponsor to discuss this.

Amendments to the protocol may only be made with the approval of the Sponsor. A protocol amendment may be subject to review by the assigned REC, Health Research Authority (HRA) and the MHRA. Written documentation of the Ethics Committee and HRA (and if appropriate the MHRA) 'favourable opinion' (i.e. approval) must be received before the amendment can be implemented and incorporated into the protocol if necessary.

15.5 Serious Breach of GCP

A serious breach is a breach which is likely to effect to a significant degree: the safety or physical or mental integrity of the subjects of the trial, or the scientific value of the trial.

In order that the Sponsor can fulfil their obligations in terms of reporting serious breaches of GCP to the MHRA within seven calendar days of identification, site staff must inform the Sponsor of any unplanned deviations to the trial protocol (or GCP principles) as soon as possible after the deviation occurs to allow prompt evaluation by the Sponsor.

16 ETHICAL CONSIDERATIONS

Before starting the trial, the protocol and ICD must receive the favourable opinion of the REC.

It is the Chief/Principal Investigator's responsibility to update patients (or their authorised representatives, if applicable) whenever new information (in nature or severity) becomes available that might affect the patient's willingness to continue in the trial. The CI/PI must ensure this is documented in the patient's medical notes and the patient is re-consented.

The Sponsor and CI/PI must ensure that the trial is carried out in accordance with the GCP principles and requirements of the UK Clinical Trials regulations (SI 2004/1031 and SI 2006/1928 as amended), the ICH GCP guidelines and the WMA Declaration of Helsinki - Ethical Principles for Medical Research Involving Human Subjects adopted by the 18th WMA General Assembly, Helsinki, Finland, June 1964 and all subsequent amendments including Oct 2013.

16.1 Approvals

The protocol, ICD and any proposed advertising material will be submitted as appropriate to the REC, regulatory authorities (MHRA in the UK), and host institution(s) for written approval.

The Sponsor will submit and, where necessary, obtain approval from the above parties for all substantial amendments to the original approved documents.

16.2 Patient confidentiality

The trial staff will ensure that the patients' anonymity is maintained. The patients will be identified only by initials and patient ID number on worksheets and any electronic database. Patient names and telephone numbers will be stored securely at each NHS Trust/Board by the clinical trial team and will only be accessible by the clinical trial team at site. All documents will be stored securely and only accessible by trial staff and authorised personnel.

The collection and processing of personal data from the patients enrolled in this clinical trial will be limited to those data that are necessary to investigate the efficacy, safety, quality and usefulness of the drug used in this trial. The data must be collected and processed with adequate precautions to ensure patient confidentiality and compliance with applicable data privacy protection according to the applicable data protection regulations. The data collected will comply with the EU General Data Protection Regulation (GDPR) 2016/679 on the protection of individuals with regard to the processing of personal data and the Data Protection Act (DPA), 2018.

Patients who agree to use the Medidata app will not be required to enter any personal data into the app other than their vital signs and responses to the questionnaire.

For long term follow up, patients will be asked to explicitly consent to this on the ICD.

16.3 Indemnity

This trial is sponsored by CR UK and therefore injury to a patient caused by the compounds under trial will not carry with it the right to seek compensation from the pharmaceutical industry. CR UK will provide patients with compensation for adverse side effects, in accordance with the principles set out in the Association of the British Pharmaceutical Industry (ABPI) guidelines on compensation for medicine-induced injury.

18 APPENDICES

h
u
n
h
lt

18.3 Appendix 3: New York Heart Association (NYHA) scale

Class I –	Patients with cardiac disease but without resulting limitation of physical activity; ordinary physical activity does not cause undue dyspnoea (or fatigue, palpitation or anginal pain).
Class II –	Patients with cardiac disease resulting in slight limitation of physical activity; they are comfortable at rest; ordinary physical activity results in dyspnoea (or fatigue, palpitation or anginal pain).
Class III –	Patients with cardiac disease resulting in marked limitations of physical activity; they are comfortable at rest; less than ordinary physical activity causes dyspnoea (or fatigue, palpitation or anginal pain).
Class IV –	Patients with cardiac disease resulting in inability to carry out physical activity without discomfort; symptoms of dyspnoea (or of angina) may be present even at rest; if any physical activity is undertaken, discomfort is increased.

18.4 Appendix 4: COVID-age calculation

<https://alama.org.uk/covid-19-medical-risk-assessment/> (last accessed April 2021).

The COVID-age calculation tool authored by the Association of Local Authority Medical Advisors (ALAMA), will be collected for the SPIKE1 trial during on trial assessments.

The tool was originally created to help assess an individual's vulnerability to COVID-19 as part of an occupational health assessment of fitness for work. It is not intended for use in clinical treatment pathways. As new scientific evidence becomes available, its estimates of vulnerability may change.

COVID-age helps assess an individual's vulnerability to COVID-19. It is based on published evidence for the main identified risk factors.

COVID-age summarises vulnerability for combinations of risk factors including age, sex and ethnicity and various health problems. It works by "translating" the risk associated with each factor into years which are added to (or subtracted from) an individual's actual age. This then gives a single overall measure of vulnerability. It can be used in people with no underlying medical conditions or multiple medical conditions. One measure combines all of an individual's risk factors with their actual age.

COVID-age is translated into a risk level of low, moderate, high and very high. This score of moderate, high or very high, will be collected from participants in the SPIKE1 trial.

There are times when the internet is not available or the ALAMA website goes down for maintenance. The risk tables can be downloaded as an Excel spreadsheet calculator in the link above.

2. INTRODUCTION

This document explains in detail the reporting analyses that will be carried out for SPIKE-1.

The analyses described in this RAP are based upon and supplement those described in the current study protocol.

To support reproducibility of the research, a clear and comprehensive account of pre-planned reporting (or statistical) analyses must be available. This RAP will establish the essential items to be considered for interim and/or final reporting requirements within the CSR and for the results upload to clinicaltrials.gov.

3. TRIAL OBJECTIVES

Primary Objective and Endpoint	
Objective	Endpoint
To further assess the safety and toxicity profile of camostat, to support integration into a Phase III trial.	Causality and severity of each adverse event (AE) to camostat.
Secondary Objectives and Endpoints	
Objective	Endpoint
To confirm that the PK profile aligns with the established PK profile for the active metabolite of camostat, 4-(4-Guanidinobenzyloxy)phenylacetic acid (GBPA).	Confirm PK parameters of GBPA as assessed by population estimates from population PK analysis (popPK).
To assess the ability of camostat to reduce the requirement for COVID-19 related hospital admission in community patients with SARS-CoV-2 infection.	Rate of COVID-19 related hospital admission in community patients with SARS-CoV-2 infection.
To evaluate the requirement for supplementary oxygen (non-invasive or mechanical invasive) in patients who have received camostat as treatment for SARS-CoV-2 infection.	Supplementary oxygen-free days at 28 days (from randomisation).
To evaluate the requirement for ventilation in patients who have received camostat as treatment for SARS-CoV-2 infection.	Ventilator-free days at 28 days (from randomisation).
To evaluate efficacy of camostat by effect on COVID-19 related clinical improvement.	
Time Frame: Days 1-28
 
Time to worst point on the scale or deterioration of two points or more (from randomisation) on a 9-point category ordinal scale.
 
9-point category ordinal scale:
 
 0. Uninfected, no clinical or virological evidence of infection 1. Ambulatory, no limitation of activities 2. Ambulatory, limitation of activities 3. Hospitalised – mild disease, no oxygen therapy 4. Hospitalised – mild disease, oxygen by mask or nasal prongs 5. Hospitalised – severe disease, non-invasive ventilation or high-flow oxygen

	
 6. Hospitalised – severe disease, intubation and mechanical ventilation 7. Hospitalised – severe disease, ventilation and additional organ support – vasopressors, renal replacement therapy (RRT), extracorporeal membrane oxygenation (ECMO) 8. Death
Research Objectives and Endpoints	
Objective	Endpoint
[REDACTED]	
 - [REDACTED] - [REDACTED] - [REDACTED] - [REDACTED]
[REDACTED]	
 - [REDACTED] - [REDACTED] - [REDACTED] - [REDACTED]
[REDACTED]	
 - [REDACTED] - [REDACTED] - [REDACTED] - [REDACTED]

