6.1 Inclusion Criteria

1. Patient willing and able to give informed consent.
2. Adults, 18 years of age and above
3. Symptomatic COVID-19 infection
4. Evidence of current COVID-19 infection from a validated assay.

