8.3.1 Days 1-14: Daily monitoring via video or phone call

Community patients will be monitored via video or phone call daily. If feasible for hospital patients daily monitoring will be performed face to face.

- [REDACTED]
- [REDACTED]
- [REDACTED]
- [REDACTED]

Number of patients asked to perform this test and days of testing may be adapted based on test availability.

- [REDACTED]
- Ordinal scale status assessment (as per secondary endpoint).

Those patients who have consented can enter their data

[REDACTED] on the Medidata patient application 'app'.

The video (phone) calls made to the patient may be recorded for quality assurance purposes. Patients will be asked to consent to recording of their calls during the main consenting process and at the beginning of each call, the patient will be asked to verbally confirm their consent. These recordings will be emailed immediately afterwards to a secure NHS email address where they will be stored securely on the NHS server until the end of the trial. See Section 14.3.1. This is not a requirement of trial participation but a proposed way of supporting the patient's participation on the trial.

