13 DATA ANALYSIS AND STATISTICAL CONSIDERATIONS

13.1 Description of statistical methods

All statistical aspects of the study will be fully documented in a comprehensive Statistical Analysis Plan authored by the study statistician and agreed by the independent Trial Steering Committee.

The primary outcome will be an exploration of camostat safety and toxicity, in terms of the number and severity of AEs and SAEs.

Descriptive statistics will be used to describe the demographics for each randomised group and overall. For categorical data, frequencies will be reported, and for continuous variables means and standard deviations, or for skewed data, medians and interquartile ranges will be reported.

Secondary outcomes will be reported in a similar way to the demographic data, with an estimate of the difference and standard error between the treatment groups for continuous or ordinal scale data. Medians and IQRs will be used where data are non-normally distributed. Absolute percentage difference and standard error will be reported for binary variables. Kaplan-Meier plots and life tables will be used to estimate median survival times

Subgroups will be explored where there are sufficient patients in each group. Data will be split by age (< 65 years vs ≥ 65 years), fall in lymphocyte ($<20\%$ fall vs $\geq 20\%$ fall), and neutrophil:lymphocyte ratio (<2.18 vs ≥ 2.18) for key explanatory variables.

No significance testing will be performed. Differences between treatment groups will be reported solely to inform future trials.

All enrolled patients who receive at least one dose of camostat in the treatment arm and complete Day 1 in the control arm will be evaluable for safety.

In order to be evaluable for efficacy, treatment arm patients must receive camostat for a minimum of five days, and control arm patients must either complete up to Day 14 or come off trial at an earlier timepoint due to an endpoint (e.g. hospitalisation).

Safety data will be collected from the date of written, or verbal, consent. Safety variables will be summarised by descriptive statistics.

Adverse events will be reported as tables of frequency of AEs by MedDRA system organ class and by worst severity grade observed. Tables should indicate related and unrelated events

Adverse events will be reported for each arm and presented as tables of frequency of AEs by MedDRA system organ class and by worst severity grade observed. Tables should indicate related and unrelated events.

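### A two-point deterioration is a different clinical event for each Day 1 score, and no planned between-arm summary uses that score, although Table 10 lists it (minor)

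*SAP*

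**What the plan says.** The endpoint has the same wording in Protocol section 4 and in RAP sections 3 and 6.9: "Time to worst point on the scale or deterioration of two points or more (from randomisation) on a 9-point category ordinal scale". The scale steps that matter here are:

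- Score 1: at home and not limited in activity
- Score 2: "Ambulatory, limitation of activities"
- Score 3, the first hospitalised step: "Hospitalised – mild disease, no oxygen therapy"
- Score 4: admitted and given oxygen by mask or prongs

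Entry requires "Symptomatic COVID-19 infection" (Protocol section 6.1) and sets no starting score. Inpatients admitted for reasons other than COVID-19 may also enter (Protocol section 9.1.4; RAP section 4).

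For secondary outcomes, Protocol section 13.1 and the SAP appendix, section 10, plan summaries by group "with an estimate of the difference and standard error between the treatment groups for continuous or ordinal scale data", with an absolute percentage difference and its standard error for binary variables. SAP sections 12.2 and 12.4 and RAP section 7.4 specify the median and range of time to worst point. Section 12.4 adds a Kaplan-Meier plot by arm. Randomisation strata are sex by age at 65 years. The other subgroups are lymphocyte fall and neutrophil:lymphocyte ratio (SAP section 11.4).

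The Day 1 score appears in one planned output, the per-patient Table 10 in RAP section 6.9. That table also has a yes/no deterioration column, which is worded for a rise exceeding two points.

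**The concern.** A change from baseline on an ordinal scale has a constant meaning only if equal steps mean equal things. Here they do not. A step from 1 to 2 is a change in activity at home, from 2 to 3 an admission, and from 3 to 4 the start of oxygen. A fixed rise of two steps therefore selects a different event for each starting point. A proportion pooled over starting scores is not the rate of any one event and varies with the case mix at entry.

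This matters because Protocol section 13.1 says that between-group differences are reported only to inform future trials. The endpoint is also a registry outcome measure (RAP section 7.4). Anyone who plans a trial from the pooled figure, or sets it beside another camostat trial, would need the mix of starting scores to read it.

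There is also a question of balance. Day 1 score is not a stratification factor. The secondary analyses use the efficacy population (RAP section 5.1; SAP section 11.1), which requires five days of camostat in one arm, and Day 14 or an endpoint in the other. Randomisation does not guarantee balance in a set chosen that way.

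**Working it through.** **The plan's own figures.** The plan gives no event rate, effect size or power for this endpoint. Its only sample-size figure is the precision of the recruitment rate (Protocol section 13.2): standard error 3.5%, which reproduces with 200 approached as √(0.5 × 0.5 / 200) = 3.5%. It has no bearing here.

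**Step 1: the threshold for each starting score.** The smallest score that qualifies is the start plus 2 under the endpoint wording, and the start plus 3 under Table 10's wording.

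| Day 1 score | Endpoint (rise of at least 2) | Table 10 (rise exceeding 2) |
|---|---|---|
| 1 | 3: admitted, no oxygen | 4: oxygen by mask or prongs |
| 2 | 4: oxygen by mask or prongs | 5: non-invasive ventilation or high-flow oxygen |
| 3 | 5: non-invasive ventilation or high-flow oxygen | 6: intubation |
| 6 | 8: death | not possible |
| 7 | not possible | not possible |

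Admission without oxygen is 3 − 1 = 2 from a start of 1, which counts. It is 3 − 2 = 1 from a start of 2, which does not. Under Table 10's wording it counts from neither, but the threshold still moves with the start. The documents do not say how an inpatient admitted for another reason is scored on Day 1. If scored in a hospitalised category, that patient starts at 3 or above.

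**Step 2: possible size.** All rates here are assumptions: 50 per arm, half starting at 1 and half at 2, 10% admitted whatever the start, and half of those admitted never on oxygen.

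- Risk of a counted deterioration: 10% from a start of 1, and 10% × 0.5 = 5% from a start of 2. The average is 7.5%, or 50 × 0.075 = 3.75 expected events per arm.
- Admissions not counted only because of the start: 50 × 0.5 × 0.10 × 0.5 = 1.25 of 5 expected per arm (25%).
- Shift in the crude difference with no drug effect: (10% − 5%) × imbalance. A 10-point imbalance gives 0.5 point, and a 20-point imbalance 1.0 point.
- Standard error of the crude difference: √(2 × 0.075 × 0.925 / 50) = 5.3 points. The shifts are 0.5 / 5.3 ≈ 0.1 and 1.0 / 5.3 ≈ 0.2 of a standard error.

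With 20% admitted, the shifts double to 1.0 and 2.0 points, and the standard error becomes √(2 × 0.15 × 0.85 / 50) = 7.1 points. The ratios are then about 0.14 and 0.28.

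**Step 3: chance of such an imbalance among all randomised patients.** Suppose 30% to 70% of 100 patients start at 2 and allocation ignores the score. A hypergeometric calculation then gives a 27% to 32% chance of at least 10 points in either direction, and a 5% to 7% chance of at least 20. With half at each score, the standard deviation of the imbalance is √(2 × 0.25 / 50) = 10 points. That is a 0.5-point shift, or (0.5 / 5.3)² ≈ 0.9% of the variance of the difference.

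These chances apply to the randomised set. The documents give nothing from which to size an imbalance in the efficacy population.

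**The case against.** The strongest reply is that no listed output gives a between-arm difference in two-point deterioration. The SAP outputs and the registry table present time to worst point, Table 11 has no deterioration row, and the flag appears only in a per-patient table. This stands. A pooled difference follows only if the general sentences of Protocol section 13.1 are applied to the flag.

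A reader might infer that the rule biases the treatment comparison or could produce a false drug effect. The documents do not support that. Randomisation leaves the crude difference among all randomised patients unbiased, no significance test is planned in Protocol section 13.1, and the shifts above are a small fraction of the standard error.

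A reader might also infer that admissions of patients starting at 2 are lost. They are not. COVID-19 related admission in community patients is a separate secondary endpoint with its own rows in Table 11. A move from 2 to 3 also still gives a worst point of 3 and a time to it. For the same reason, a further outcome of first reaching 3 or above is not needed.

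It is also fair that few events would be spread thinly over strata. That limits a stratified estimate, but not a table of counts.

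The appeal to randomisation is weaker for the efficacy population, whose selection rules differ by arm. The SAP's intention-to-treat analysis of the main secondary outcomes would help, but it is conditional on the data allowing it (SAP section 11.1).

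**Conclusion.** The point holds as one of interpretation. The threshold arithmetic is exact: the two-point criterion means admission without oxygen from 1, oxygen from 2, and non-invasive ventilation or high-flow oxygen from 3. No planned between-arm summary uses the Day 1 score.

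The numerical effect is small: 0.5 to 1.0 point against a standard error of about 5.3 points, or 1.0 to 2.0 against 7.1 if admissions are twice as common. These figures rest on assumed admission and oxygen rates, an assumed even split of starting scores, and equal admission risk from scores 1 and 2. None of these is in the documents. Imbalance in the efficacy population is a possibility that the documents do not allow one to size.

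The mismatch between Table 10's flag and the endpoint is a plain inconsistency and decides which thresholds apply. The severity is minor: the endpoint is secondary and descriptive, and the sample size does not rest on it.

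**What to change.** In RAP section 6.9 and SAP section 12.4:

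1. Reconcile Table 10's deterioration column with the endpoint, so that one threshold is used throughout.
2. Add one table with counts and denominators for two-point deterioration, by arm within Day 1 score (1, 2, 3 or above).
3. Where numbers allow, give a between-arm difference stratified by Day 1 score (for example a Mantel-Haenszel risk difference), with its standard error or 95% confidence interval, beside the crude one. If the stratum at 3 or above is sparse, report counts only.

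The cost is a wording change in the RAP and SAP and one table. The Day 1 score is already collected, so no new data, visits or patients are needed.
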